6.5.7.6 Sensitivity Analyses

6.5.7.6.1 Sensitivity Analyses for Primary Efficacy Endpoints

Two-sample t-tests (equal variance assumed), Wilcoxon rank sum tests and mixed-effect repeated measures analysis comparing treatment groups will be performed as sensitivity analyses. The mixed-effect repeated measures model will include treatment, baseline value, visit, and the interaction between treatment and visit as fixed effects, and subject as a random effect. An unstructured covariance matrix will initially be used to model the covariance among repeated measures; however, if the model fails to converge using this covariance structure, either heterogeneous TOEPLITZ, homogeneous TOEPLITZ, or compound symmetry will be implemented according to the Akaike information criterion with a correction for finite sample sizes (AICc).

Sample SAS two-sample t-test code:

```
PROC TTEST DATA=INDATA;
  CLASS <TREATMENT>;
  VAR <ENDPOINT>;
RUN;
```

Sample SAS Wilcoxon rank sum test code:

```
PROC NPAR1WAY DATA=INDATA WILCOXON;
  CLASS <TREATMENT>;
  VAR <ENDPOINT>;
RUN;
```

Sample SAS mixed-effect repeated measures analysis code:

```
PROC MIXED DATA=INDATA;

CLASS <TREATMENT> <VISIT> <SUBJECT>;

MODEL <ENDPOINT>=<TREATMENT> <VISIT> <TREATMENT>*<VISIT> <BASELINE>;

REPEATED <VISIT> / SUBJECT=<SUBJECT> TYPE=UN;

RANDOM <SUBJECT>;

ESTIMATE 'NOV03-SALINE' <TREATMENT> -1 1 / ALPHA=0.05 CL;

RUN;
```

Where 'Saline' is <TREATMENT>=0 and 'NOV03' is <TREATMENT>=1.

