Least squares mean for each treatment group and for the difference between treatment groups will be presented from each model together with two-sided p-values (used for primary inference) and 95% confidence intervals.

Two-sample t-tests, Wilcoxon rank sum tests and mixed-effect repeated measures analysis comparing treatment groups will be performed as sensitivity analyses. The mixed-effect repeated measures model will include treatment, baseline value, visit, and the interaction between treatment and visit as fixed effects, and subject as a random effect. An unstructured

covariance matrix will initially be used to model the covariance among repeated measures; however, if the model fails to converge using this covariance structure, either heterogeneous TOEPLITZ, homogeneous TOEPLITZ, or compound symmetry will be implemented according to the Akaike information criterion with a correction for finite sample sizes (AICc).

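### The MMRM sensitivity model pairs a random subject effect with an unstructured covariance that already contains it, so a needless convergence failure could change the covariance used

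*SAP*

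**What the plan says.** SAP 6.5.7.6.1 describes a repeated-measures model with treatment, baseline value and visit "and the interaction between treatment and visit as fixed effects, and subject as a random effect". It continues: "An unstructured covariance matrix will initially be used to model the covariance among repeated measures". The sample PROC MIXED call carries out both instructions, with "REPEATED <VISIT> / SUBJECT=<SUBJECT> TYPE=UN" and "RANDOM <SUBJECT>" in the same step. There is also a contingency: "if the model fails to converge using this covariance structure, either heterogeneous TOEPLITZ, homogeneous TOEPLITZ, or compound symmetry will be implemented", chosen by AICc.

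SAP 6.5.7.6.2 repeats the model for the secondary endpoints. SAP 6.5.7.6.3 calls for an MMRM on the other quantitative endpoints without restating it. Protocol 10.4.5 has the same pairing, listing the other terms "as fixed effects, and subject as a random effect".

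Neither document drops the random effect at any step, including in the fallback, and neither defines failure to converge.

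**The concern.** A random subject intercept adds one constant to every variance and covariance among a subject's visits. An unstructured matrix leaves all of those elements free already, so the constant can be moved between the two parts without changing the fitted model. The data can estimate only the sum.

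This would be harmless surplus if nothing depended on how the fit ended. Here the SAP attaches a rule to it: "if the model fails to converge using this covariance structure", the covariance structure changes. An over-parameterised fit may end with the surplus variance at zero, or with a non-convergence message or singular Hessian. In the second case a pre-specified analysis could leave the unstructured matrix because of a fault in its own specification, although the unstructured model by itself is identified. The standard error, and the weight given to subjects with only early visits, would then depend on optimiser behaviour and on how a log message is read.

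**Working it through.** **Inputs.** There are three post-baseline visits, Days 15, 29 and 57 (Protocol 4.3). The response is change from baseline (SAP 6.5.8.3) with baseline as a covariate, so baseline is not a fourth repeated measure. The covariance specification is in SAP 6.5.7.6.1. The plan gives no figure for this model to reproduce.

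**Marginal covariance.** With random-intercept variance σ_b², residual matrix R and J the matrix of ones, V = σ_b²·J + R. Only V enters the likelihood.

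**Unstructured R.** R has 3 × 4 / 2 = 6 free elements, and adding σ_b² makes 7 parameters. For any c, replacing (σ_b², R) by (σ_b² − c, R + c·J) leaves V unchanged. V has 6 distinct elements, so one parameter is not identified.

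**Fallback structures, random effect kept.** The ranks are those of the numerical Jacobian of the six distinct elements of V with respect to the parameters.

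| Structure of R | Parameters including σ_b² | Rank |
|---|---|---|
| Unstructured | 6 + 1 = 7 | 6 |
| Homogeneous Toeplitz | 3 + 1 = 4 | 3 |
| Compound symmetry | 2 + 1 = 3 | 2 |
| Heterogeneous Toeplitz | 5 + 1 = 6 | 6, or 5 if the Day 15 and Day 57 SDs are equal |

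For homogeneous Toeplitz, V has one value per lag (0, 1, 2), each shifted by σ_b²: three values from four parameters. For compound symmetry, σ_b² adds directly to the common covariance.

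Heterogeneous Toeplitz needs more care. Its restriction is equal correlation for the two adjacent visit pairs, so σ_b² is determined only through (V₁₂ − σ_b²)/(V₂₃ − σ_b²) = √[(V₁₁ − σ_b²)/(V₃₃ − σ_b²)]. When the first and third SDs are equal, V₁₁ = V₃₃ and V₁₂ = V₂₃, both sides equal 1 for every σ_b², and identification is lost. At assumed SDs of 2.5, 2.8 and 3.0, correlations of 0.4 and 0.3, and σ_b² = 1, the rank is 6, but the smallest singular value is 0.07 against a largest of 11.28.

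**Other numbers of visits.** The unstructured model with a random subject has 11 parameters and rank 10 at four visits, and 37 and 36 at eight.

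**Likelihood check.** One dataset was simulated: 500 subjects, SD 2.8 at each visit (the SAP's tCFS figure), and assumed covariances of 4.3 for adjacent visits and 3.5 for Day 15 with Day 57. The negative log-likelihood, constant omitted, was 2112.1032 at σ_b² = 0, 0.5, 1, 2 and 3, with R positive definite each time. The ridge is exactly flat. The smallest Hessian eigenvalue was 0 with the random effect and 1.44 without it, at the same maximised likelihood.

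**Size if the fallback is used.** A small simulation took 560 subjects, SD about 2.8, 10% dropout (the SAP's rate) and assumed correlations of 0.5 to 0.6, with 8 datasets under each of two visit-SD patterns. Against the unstructured model alone, the AICc-chosen fallback moved the Day 57 tCFS difference by at most 0.005, with a standard-error ratio of 0.96 to 1.02. With SDs of 2.5, 2.8 and 3.0, AICc always chose heterogeneous Toeplitz and the ratio was 0.996 to 1.000.

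**The case against.** The strongest reply is that nothing decisive rests on this model. Primary inference is by ANCOVA (SAP 6.5.7.3). The MMRM sits beside t-tests and Wilcoxon tests as a sensitivity analysis, in addition to the per-protocol, LOCF and multiple-imputation analyses. No success rule, hierarchical step or power figure uses it. The harm is also conditional: a redundant variance set to zero is not failure to converge, and the documents do not show that failure is likely. If the fallback is reached, AICc selection gives some protection against a poorly fitting structure, and the simulated effect was small. All of this stands and limits the weight of the point. It does not show that the specification is sound, since the random term adds nothing to the fit.

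A reader might infer more than the documents support:

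- *Three visits are too few.* They are not the cause; the redundancy is the same at any number of visits.
- *Heterogeneous Toeplitz is a clean way out.* With the random effect kept, it is weakly identified at best.
- *The common baseline slope and unspecified degrees-of-freedom method are part of the error.* A common slope is a legitimate model, and nothing in the plan requires this MMRM to reproduce the Day 57 ANCOVA. A baseline-by-visit term and Kenward-Roger degrees of freedom are optional choices.

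**Conclusion.** The specification is wrong as written, in text and code, but the consequence is limited. The redundancy is certain: 7 parameters for 6 identifiable elements in the initial model, and 4 for 3 and 3 for 2 in two of the fallbacks. Whether it causes harm depends on the software and on what the team counts as failure to converge; the documents settle neither. A converged fit gives the same marginal covariance and treatment estimates as the unstructured model alone.

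The exposure covers the MMRM sensitivity analyses of both primary endpoints, the four secondary endpoints and, by extension, the other quantitative endpoints. The effect on any estimate is probably small, but that rests on a few simulated datasets with assumed correlations. The reading of the fallbacks assumes that the random effect stays in them, since nothing removes it. A reader might infer that the primary result or the type I error control is at risk; neither uses this model.

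**What to change.** In SAP 6.5.7.6.1, delete the clause that makes subject a random effect and the code line "RANDOM <SUBJECT>". Make the matching deletion in 6.5.7.6.2. Keep "REPEATED <VISIT> / SUBJECT=<SUBJECT> TYPE=UN", which with three visits has 6 parameters for 6 elements. State that the fallback structures are fitted without a random effect, and only if this unstructured model fails to converge. A sentence defining failure to converge would also help.

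SAP 6.6 currently records no changes to the planned analyses; note the departure from Protocol 10.4.5 there. The cost is wording in these SAP sections and one line of code. Data collection, sample size and the primary analysis are unaffected. SAP section 4 allows such a change by amendment before database lock and unmasking; afterwards, a change of covariance would look post hoc.

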5 TRIAL OBJECTIVES

5.1 Primary Objective

The primary objective of this trial is to assess the efficacy of NOV03 (perfluorohexyloctane) ophthalmic solution at a QID dosing regimen in comparison to a saline control for the treatment of the signs and symptoms of DED

The population-level summaries of the primary estimands are:

- Difference in mean CFB of tCFS score (NEI scale) at Day 57 (NOV03 minus saline)
- Difference in mean CFB of Dryness Score (VAS Severity of Dryness) at Day 57 (NOV03 minus saline)

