6.4 Efficacy and Safety Variables

6.4.1 Efficacy Variables

6.4.1.1 Primary Efficacy Endpoints

Two primary endpoints will be tested in the following order using hierarchical fixed sequence testing:

- 1. Change from baseline (CFB) in tCFS (NEI scale) at Day 57
- 2. CFB of Dryness Score (VAS Severity of Dryness) at Day 57

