6.5.7.3 Primary Efficacy Analyses

The primary comparisons in this trial will be between NOV03 versus saline at Day 57 in the FAS with available data per subject using the following estimands

- Endpoint:
 - CFB in tCFS in the study eye at Day 57
 - CFB of Dryness Score (VAS) at Day 57
- Intercurrent event:
 - Discontinuation of study medications is ignored. [treatment policy strategy]
 - Non-optimal compliance is ignored. [treatment policy strategy]
 - Withdrawal due to any reason. Missing data not imputed. [hypothetical strategy if overall study discontinuation rate is <5%]
- Population-level summary:
 - Difference in the mean CFB in tCFS in the study eye at Day 57 between NOV03 and saline
 - Difference in the mean CFB of Dryness Score (VAS) at Day 57 between NOV03 and saline

If the overall study discontinuation rate in the FAS is \geq 5% then the primary analysis will be based on imputation methodology using the following estimands:

• Endpoint:

Protocol Number: 904

- CFB in tCFS in the study eye at Day 57
- CFB of Dryness Score (VAS scale) at Day 57

• Intercurrent event:

- Discontinuation of study medications is ignored. [treatment policy strategy]
- Non-optimal compliance is ignored. [treatment policy strategy]
- Withdrawal due to lack of efficacy or adverse events: baseline observation carried forward (BOCF) is used to impute missing data [hypothetical strategy if overall study discontinuation rate ≥5%]
- Missing data without withdrawal or withdrawal due to reasons other than lack of efficacy or adverse events: multiple imputations using randomized treatment-based Markov Chain Monte Carlo (MCMC) is used to impute missing data [hypothetical strategy if overall study discontinuation rate ≥5%]
- Population-level summary:
 - Difference in the mean CFB in tCFS in the study eye at Day 57 between NOV03 and saline
 - Difference in the mean CFB of Dryness Score (VAS scale) at Day 57 between NOV03 and saline

The primary comparison in this trial will be between NOV03 versus saline at Day 57. The primary efficacy endpoints (e.g. CFB in total corneal fluorescein staining [NEI scale] and Dryness Score) will be tested using hierarchical fixed sequence testing and summarized descriptively (n, mean, standard deviation, median, min, and max) and analyzed separately using an ANCOVA model with terms for baseline value, and treatment.

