7 INDEX OF PLANNED TABLES, FIGURES, AND LISTINGS

Title
Overall Disposition and Subject Accountability – FAS
Overall Disposition and Subject Accountability – PPS
Overall Disposition and Subject Accountability – SAF
Overview of Analysis Sets – Randomized Subjects
Reasons for Exclusion from Study Populations – Randomized Subjects
Major Protocol Deviations – FAS
Demographic and Baseline Characteristics – FAS
Demographic and Baseline Characteristics – PPS
Demographic and Baseline Characteristics – SAF
Baseline Ocular Characteristics – FAS
Baseline Ocular Characteristics – PPS
Baseline Ocular Characteristics – SAF
Study Eye Ocular Medical History – FAS
Fellow Eye Ocular Medical History – FAS
Subject Level Ocular Medical History – FAS
Non-ocular Medical History – FAS
Study Eye Ocular Concomitant Medications – FAS
Fellow Eye Ocular Concomitant Medications – FAS
Subject Level Ocular Concomitant Medications – FAS
Non-ocular Concomitant Medications – FAS
Study Medication Exposure and Compliance – SAF
Analyses of Change from Baseline tCFS and Dryness Score (VAS) at Day 57 – FAS
Analyses of Change from Baseline tCFS and Dryness Score (VAS) at Day 57 – PPS
Robustness Analyses of Change from Baseline tCFS and Dryness Score (VAS) at Day 57 (Discontinuation Rate ≥5%) – FAS
Sensitivity Analyses of Change from Baseline tCFS and Dryness Score (VAS) at Day 57 – FAS
Analyses of Secondary Efficacy Endpoints – FAS
Sensitivity Analyses of Secondary Efficacy Endpoints – FAS
Analysis of Dryness Score (VAS) – FAS
Sensitivity Analysis of Dryness Score (VAS) – FAS
Analysis of Study Eye tCFS – FAS

- 14.2.6.2 Analysis of Fellow Eye tCFS – FAS
- 14.2.6.3 Sensitivity Analysis of Study Eye tCFS – FAS
- Sensitivity Analysis of Fellow Eye tCFS FAS 14.2.6.4
- 14.2.7.1 Analysis of Study Eye Central Sub-region CFS (NEI scale) – FAS
- Analysis of Fellow Eye Central Sub-region CFS (NEI scale) FAS 14.2.7.2
- 14.2.7.3 Sensitivity Analysis of Study Eye Central Sub-region CFS (NEI scale) – FAS
- 14.2.7.4 Sensitivity Analysis of Fellow Eye Central Sub-region CFS (NEI scale) – FAS
- 14.2.7.5 Analysis of Study Eye Inferior Sub-region CFS (NEI scale) – FAS
- 14.2.7.6 Analysis of Fellow Eye Inferior Sub-region CFS (NEI scale) – FAS
- 14.2.7.7 Sensitivity Analysis of Study Eye Inferior Sub-region CFS (NEI scale) – FAS
- Sensitivity Analysis of Fellow Eye Inferior Sub-region CFS (NEI scale) FAS 14.2.7.8
- Summary of Study Eye CFS by Sub-region (NEI scale) FAS 14.2.8.1

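### The sample repeated-measures code has no Day 57 treatment contrast, although the table it feeds is for Day 57

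*SAP*

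**What the plan says.** SAP 6.5.7.6.1 lists t-tests, Wilcoxon tests and a mixed-effect repeated measures model as sensitivity analyses for the primary endpoints. The sample code for the repeated measures model declares "CLASS <TREATMENT> <VISIT> <SUBJECT>" and fits "MODEL <ENDPOINT>=<TREATMENT> <VISIT> <TREATMENT>*<VISIT> <BASELINE>". The only treatment comparison requested is "ESTIMATE 'NOV03-SALINE' <TREATMENT> -1 1 / ALPHA=0.05 CL". The note below the code, "Where 'Saline' is <TREATMENT>=0 and 'NOV03' is <TREATMENT>=1", fixes the sign as NOV03 minus saline. The code has no LSMEANS statement and no second ESTIMATE.

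The target that this analysis should support is stated several times, always at Day 57:

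- SAP 6.4.1.1, first primary endpoint: "Change from baseline (CFB) in tCFS (NEI scale) at Day 57". The second, Dryness Score, is also at Day 57.
- SAP 5.1, estimand summary: "Difference in mean CFB of tCFS score (NEI scale) at Day 57 (NOV03 minus saline".
- SAP 6.5.7.3, population-level summary: "Difference in the mean CFB in tCFS in the study eye at Day 57 between NOV03 and saline".
- SAP 7, planned output: "Sensitivity Analyses of Change from Baseline tCFS and Dryness Score (VAS) at Day 57".

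The prose on this model in Protocol 10.4.5 and SAP 6.5.7.6.1 lists the fixed effects but does not say at which visit the treatments are compared. SAP 6.5.7.6.2 and 6.5.7.6.3 call for the same kind of model for the secondary and other endpoints, with no code and no contrast.

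**The concern.** The interaction term lets the treatment effect differ between visits. A contrast on the treatment main effect alone does not pick out one of those visits. The t-test and Wilcoxon samples can be made Day 57 analyses by restricting the input data to Day 57. The repeated measures model cannot, because it needs several visits, so the visit has to be chosen in the contrast.

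If the code is run as written and returns an estimate, the repeated measures row of a Day 57 table would hold a visit-averaged difference with its own standard error. A reader would take it as a check on the Day 57 ANCOVA. Agreement or disagreement between the two rows could then reflect the time course of the effect and not the robustness of the Day 57 result. The same code, reused for the secondary endpoints, would not give the Day 15 differences that the first two of them need (SAP 6.4.1.2).

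**Working it through.** **Inputs from the documents.** SAP 6.5.10: 250 per arm; tCFS difference -1.0, SD 2.8; Dryness Score difference -10, SD 28; two-sided alpha 0.05; stated power 97.9% each. Post-baseline visits: Days 15, 29 and 57 (SAP Table 1).

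**Assumptions.** The documents give no Day 15 or Day 29 effects, no between-visit correlation and no visit-specific SDs. Assumed here: SD 2.8 at every visit, a common correlation r of 0.3, 0.5 or 0.7, complete data, and several time courses that all end at -1.0.

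**Step 1, the plan's own figure.** Day 57 SE = 2.8 × √(2/250) = 0.250. Power = Φ(1.0/0.2504 − 1.96) = Φ(2.03) = 97.9%. Dryness Score has the same ratio (10/28 = 1.0/2.8), so also 97.9%. The stated power reproduces.

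**Step 2, what the contrast estimates.** Write the model in the over-parameterised form that a plain CLASS statement implies: intercept, 2 treatments, 3 visits, 6 treatment-by-visit cells, baseline. A contrast is estimable if it lies in the row space of the design matrix. All rows below have treatment coefficients -1 1. Interaction cells are ordered saline Days 15, 29, 57, then NOV03 Days 15, 29, 57.

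| Interaction coefficients | Estimable? | Quantity |
|---|---|---|
| 0 0 0 0 0 0 (literal reading) | No | none |
| -1/3 ×3, +1/3 ×3 (equal filling) | Yes | mean of the three visit differences |
| 0 0 -1 0 0 1 | Yes | Day 57 difference |
| -1 0 0 1 0 0 | Yes | Day 15 difference |

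The averaged quantity equals the Day 57 difference only if the Day 15 and Day 29 effects average to the Day 57 effect. Examples are a constant effect, or -1.2, -0.8, -1.0.

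**Step 3, precision.** Averaged SE = 2.8 × √((1+2r)/3) × √(2/250):

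- r = 0.3: 0.183, which is 27% below 0.250
- r = 0.5: 0.204, 18% below
- r = 0.7: 0.224, 11% below

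**Step 4, coverage and power.** Let b = (target + 1.0)/SE. The averaged 95% interval covers the Day 57 effect of -1.0 with probability Φ(1.96 − b) − Φ(−1.96 − b). Power is Φ(|target|/SE − 1.96), the far tail being negligible. For example, with target -0.75 and r = 0.3, b = 0.25/0.1829 = 1.367. Coverage is then Φ(0.593) − Φ(−3.327) = 72.3%, and power is Φ(4.101 − 1.96) = 98.4%.

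| Effects at Days 15 / 29 / 57 | Target | Coverage of -1.0 (r = 0.3 / 0.5 / 0.7) | Power (r = 0.3 / 0.5 / 0.7) |
|---|---|---|---|
| -1.0 / -1.0 / -1.0 | -1.0 | 95.0 / 95.0 / 95.0% | 100.0 / 99.8 / 99.4% |
| -1.2 / -1.1 / -1.0 | -1.1 | 91.5 / 92.2 / 92.7% | 100.0 / 100.0 / 99.8% |
| -0.75 / -0.875 / -1.0 | -0.875 | 89.5 / 90.6 / 91.4% | 99.8 / 99.0 / 97.4% |
| -0.5 / -0.75 / -1.0 | -0.75 | 72.3 / 76.9 / 80.0% | 98.4 / 95.6 / 91.7% |
| 0 / -0.5 / -1.0 | -0.5 | 22.0 / 31.4 / 39.3% | 78.0 / 68.6 / 60.7% |

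A Day 57 contrast has 95% coverage and 97.9% power in every row. For Dryness Score, multiply the targets by 10; coverage and power are the same.

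**Step 5, simulation.** For the -0.5 / -0.75 / -1.0 course, 4,000 simulated trials per correlation gave coverage of -1.0 by the averaged contrast of 73.1, 77.6 and 79.8%, and rejection in 98.1, 95.3 and 91.2%. The Day 57 contrast covered in 94.9, 94.7 and 94.7% and rejected in 97.8, 97.9 and 97.9%.

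**The case against.** The strongest reply is that the block is labelled as sample code with placeholders, while the section heading, the endpoint definitions and the table title all fix Day 57. A careful programmer filling that table would add the visit. This limits the likelihood of harm but does not supply the missing specification. The ESTIMATE line is the only statement in either document of which quantity this model reports. Anyone who follows it does not get Day 57, and anyone who departs from it picks the contrast without pre-specification.

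A second point is technical. Under reference-level coding with NOV03 and Day 57 as the reference levels, the bare -1 1 would be the Day 57 difference. That is true, but the code uses a plain CLASS statement and asks for no such coding. It is also fair that equal filling is an assumption about the software. If the program reported the contrast as non-estimable, the fault would show itself and no wrong number would reach the table.

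Third, every size given here depends on assumed time courses. That stands. The plan puts two Day 15 endpoints first among the secondaries, and Protocol 4.5 stresses early onset, so a near-constant effect is plausible; the target would then be correct. Significance could be little affected or clearly affected, depending on a time course that the documents do not give.

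**Conclusion.** The concern holds. As written, the repeated measures code does not produce the Day 57 treatment difference. It is either non-estimable or, with equal filling of the interaction, an average over three visits.

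The defect in the code does not depend on any assumed effect; its size does. With 250 per arm, equal SDs and correlations of 0.3 to 0.7, the interval is 11% to 27% narrower than a Day 57 interval whatever the time course. The error in the target runs from none (constant effect) through 25% too small (-0.75 for -1.0, coverage 72% to 80%) to half (-0.5, power 61% to 78%) for a slow onset. It would be too large if early effects were larger.

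The reach is limited to sensitivity analyses. The Day 57 ANCOVA that carries the primary inference, the fixed-sequence testing and the sample size are unchanged. The SAP should be corrected before unmasking, but the point does not threaten the trial's primary conclusion.

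**What to change.** In SAP 6.5.7.6.1, replace the ESTIMATE line with a Day 57 contrast:

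`ESTIMATE 'NOV03-SALINE Day 57' <TREATMENT> -1 1 <TREATMENT>*<VISIT> 0 0 -1 0 0 1 / ALPHA=0.05 CL;`

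State that visits are ordered Day 15, 29, 57 and that the existing treatment coding (saline 0, NOV03 1) applies. The same-visit difference from `LSMEANS <TREATMENT>*<VISIT>` is equivalent.

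In SAP 6.5.7.6.2 and 6.5.7.6.3, add one sentence each: the contrast is taken at the visit named in the endpoint. The interaction coefficients are -1 0 0 1 0 0 for Day 15 and 0 -1 0 0 1 0 for Day 29.

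The cost is one line of code and two sentences. The protocol names no contrast for this model, so it needs no edit. No new data and no change in sample size are needed. SAP section 4 already provides for amendments before database lock and unmasking.
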